Background about migraine and sleep: Most patients believe that many of their migraine attacks are triggered by sleeping too little, sleeping too much, have their sleep interrupted too many times during the night, poor sleep quality, not feeling well-rested in the morning hours after the sleep, etc. These common complaints gave rise to the notion that sleep disturbances are some of the most common triggers of migraine. Moreover, sleep disturbances may be a risk factor for chronification of migraine, the transformation of migraine from episodic to chronic form. If sleep disturbances can trigger migraine attacks or lead to its chronification, it is tempting to propose that drugs that prevent migraine may have an ability to restore normal sleep or attenuate certain aspects of sleep disturbances and by doing so, prevent the initiation of an attack by preventing or modifying its trigger.

Background on fremanezumab and the hypothalamus: Fremanezumab is an anti-CGRP monoclonal antibody and belongs to a class of drugs that effectively prevents migraine. In principle, the size of CGRP (about 150 kD) does not allow it to cross the blood brain barrier (BBB) and enter the brain. It is therefore believed to achieve its preventative effects by acting outside the brain. An exception to this thinking is the hypothalamus, a brain area where the BBB is relatively open and as a result, large molecules may gain some access to its neurons.

B3. DESCRIPTION OF RESEARCH PROTOCOL

A. Study Design – Overview, Methods, Procedures

Overview:

This is a within-person study design that examines treatment effects (changes) using high-resolution assessments. To complete the study, each participant will be observed using daily assessments of **migraine** and **sleep** outcomes before treatment (baseline: 0 to 30 days), and at 1, 2, and 3 months after treatment (injection 1: days 31-60, injection 2: days 61-90, injection 3: days 91-120). In essence, this creates an interrupted time-series design where repeated interventions are introduced at fixed intervals.

Methods:

The study involves 5 visits. The first and last visit will take place at the headache clinic, while the middle three will occur at the Clinical Research Center:

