Sensitivity to Missing Data: We will strive to reduce the extent of missing data by using daily diaries with low burden. Further, our estimation techniques, based on maximum likelihood, utilize all available data, and as such produce unbiased estimates when the data are missing at random (MAR). The trajectory-based approach should be robust to embedded missing data and the models include many of the factors that might produce an increased drop-out rate (e.g., lack of treatment response). Nevertheless, we will examine estimates in the context of sensitivity analyses utilizing multiple imputation procedures under a variety of assumptions, including a pain drop-out model (ie, lingering pain is associated with increased drop-out) recently implemented by [name].

C. Subject Selection

Potential study subjects will be provided an informed consent form (ICF) to review. Those who are interested in participating will provide informed consent and then be screened for eligibility (inclusion/exclusion criteria). Individuals screened as potential study subjects must meet all the following inclusion criteria and none of the following exclusion criteria.

INCLUSION CRITERIA

1. Between the ages of 18 and 65 years
2. Been previously diagnosed with migraine (with or without aura), in accordance with the ICHD-3 criteria
3. Experiences between 8 to 25 headaches days per month (during the last 3 months), with at least 8 of them being migraine days during which the migraines lasted more than 4 hours if untreated
4. Onset of migraine at age 50 years or younger

5. Agrees to refrain from initiating or changing the type, dosage, or frequency of any prophylactic medications for indications other than migraine that may interfere with the study objectives (e.g., antidepressants, anticonvulsants, beta-adrenergic blockers, etc.)
6. Able to provide written informed consent

EXCLUSION CRITERIA

1. Currently on a regimen of 1 or more migraine preventative therapy
2. Other significant pain problem (e.g., cancer pain, fibromyalgia, other head or facial pain disorder) that may confound the study assessments
3. Known or suspected severe cardiac disease (e.g., symptomatic coronary artery disease, prior myocardial infarction, congestive heart failure)
4. Known or suspected cerebrovascular disease (e.g., prior stroke or transient ischemic attack, symptomatic carotid artery disease, prior carotid endarterectomy or other vascular neck surgery)

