5. Abnormal baseline electrocardiogram (ECG) within the last year (e.g., second or third-degree heart block, prolonged QT interval, atrial fibrillation, atrial flutter, history of ventricular tachycardia or ventricular fibrillation, clinically significant premature ventricular contraction)
6. Uncontrolled high blood pressure (systolic >160 mm HG, diastolic >100 mm Hg) after 3 measurements within 24 hours
7. Known history or suspicion of secondary headache
8. Known history or suspicion of substance abuse or addiction (within the last 5 years)
9. Preventative use of marijuana (including medical marijuana) or cannabidiol oil within the last 1 year
10. Currently takes simple analgesics or NSAIDs >15 days per month or triptans, ergots, or combined analgesics >10 days per month for headaches or other body pain
11. Currently takes prescription opioids for headaches or body pain
12. Undergone nerve block (occipital or other) in the head or neck within the last 3 months
13. Received botulinum toxin or anti-CGRP-mAb injections within the last 6 months
14. Nursing, pregnant, or thinking of becoming pregnant during the study period, or of childbearing years and unwilling to use an accepted form of birth control
15. Participating in any other therapeutic clinical investigation or has participated in a clinical trial in the preceding 30 days
16. Belongs to a vulnerable population or has any condition such that his or her ability to provide informed consent, comply with the follow-up requirements, or provide self-assessments is compromised.
17. A relative of or an employee of the Investigator or the clinical study site
18. Psychiatric or cognitive disorder and/or behavioral problems that, in the opinion of the clinician, may interfere with the study
19. BMI of 30 or greater

B4. POSSIBLE BENEFITS

It is not guaranteed or promised that patients will receive any benefit from being in this study. Information from this study may help others in the future as a result of knowledge gained from the research.

B5. POSSIBLE RISKS AND ANALYSIS OF RISK/BENEFIT RATIO**HYPERSENSITIVITY REACTIONS**

Hypersensitivity reactions such as rash, urticaria, and dyspnea have been reported with fremanezumab in clinical trials. If a serious or severe hypersensitivity reaction occurs, treatment with fremanezumab will be discontinued and the subject will be treated with an appropriate therapy.

ANTICIPATED ADVERSE EVENTS

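### The stability rule for non-migraine prophylactic drugs covers only the time after enrolment, so a recent start or change before visit 1 is allowed; the resulting bias is probably small but cheap to avoid

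*Combined protocol and SAP*

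**What the plan says.** Inclusion criterion 5 in section B3.C asks that the participant "Agrees to refrain from initiating or changing the type, dosage, or frequency of any prophylactic medications for indications other than migraine", and limits this to drugs "that may interfere with the study objectives (e.g., antidepressants, anticonvulsants, beta-adrenergic blockers, etc". It is a promise about future conduct and sets no minimum period on a stable regimen before visit 1.

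The neighbouring criteria do not fill the gap:

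- Exclusion 1 removes a person who is "Currently on a regimen of 1 or more migraine preventative therapy". It does not reach the same drug taken for another indication.
- Exclusions 9, 12 and 13 look back over a stated period: "Preventative use of marijuana (including medical marijuana) or cannabidiol oil within the last 1 year", "Undergone nerve block (occipital or other) in the head or neck within the last 3 months" and "Received botulinum toxin or anti-CGRP-mAb injections within the last 6 months". None covers the drugs named in inclusion 5. Exclusion 15 has a 30-day look-back, but for participation in other trials.
- Exclusion 18 covers "Psychiatric or cognitive disorder and/or behavioral problems that, in the opinion of the clinician, may interfere with the study". It works by clinical opinion, not by the date a drug was started.

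On design, the Overview in section B3.A states: "This is a within-person study design that examines treatment effects (changes) using high-resolution assessments". There is one group, a baseline from day 0 to day 30, and three monthly injections observed to day 120. Both primary outcomes compare the treatment period with the time before it.

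**The concern.** The protocol itself classes these drugs as capable of disturbing the study's objectives, which are sleep and migraine. Section B5 also lists antidepressants, anti-epileptics and antihypertensives among the older migraine preventives. Barring a start or change during the study makes sense only if such an event could move the outcomes. A start a few days before visit 1 could do much the same, yet it is allowed.

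If the effect of such a drug is still developing when the baseline month ends, the remainder falls in the treatment months. In a single-arm comparison nothing separates it from the effect of fremanezumab. If the drug also moves sleep and migraine in the same person, it acts as a common cause of both trajectories and could add to the association that the four hypotheses interpret. The person-specific random trajectories in Data Analysis do not remove this, because the drug's effect becomes part of each person's slope. The planned sensitivity analyses concern missing data only.

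**Working it through.** **The plan's own figure.** The point rests on no stated figure. The only relevant benchmark is the target correlation between slopes, r = 0.15, from Sample Size Justification (N = 100, alpha 0.05, power 95%, 95% CI 75.1% to 99.9%). The interval equals the exact binomial interval for 19 of 20 (0.7513 to 0.9987). The power cannot be rebuilt, because the simulation model is not fully given. Neither matter affects what follows.

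**Inputs from the documents.** Baseline is days 0 to 30, treatment is days 30 to 120, N = 100, benchmark r = 0.15.

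**Assumed inputs (not in the documents).** The drug was started s = 3 to 7 days before visit 1. Its effect builds as 1 − exp(−(t + s)/τ) with τ = 7 to 42 days. Its full effect is 1 SD on both sleep and migraine, in the same direction. A share q = 5% to 20% of participants is affected.

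**Step 1: how much of the effect the baseline absorbs.** The share left in the contrast is the mean of the onset curve over days 30 to 120 minus its mean over days 0 to 30:

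share = exp(−s/τ) × τ × {[1 − exp(−30/τ)]/30 − [exp(−30/τ) − exp(−120/τ)]/90}

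| τ (days) | s = 3 | s = 7 | s = 90 |
|---|---|---|---|
| 7 | 0.149 | 0.084 | 0.000 |
| 14 | 0.318 | 0.239 | 0.001 |
| 28 | 0.459 | 0.398 | 0.021 |
| 42 | 0.478 | 0.434 | 0.060 |

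For a start 3 to 7 days before visit 1, 8% to 48% of the full effect remains. For a start 90 days before, 0% to 6% remains.

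**Step 2: bias in the mean change.** Bias = q × d, where d = full effect × share. With a full effect of 1 SD and the largest share, d = 0.478:

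- q = 5%: 0.05 × 0.478 = 0.024 SD
- q = 10%: 0.10 × 0.478 = 0.048 SD
- q = 20%: 0.20 × 0.478 = 0.096 SD

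**Step 3: spurious correlation between the two changes.** With a true correlation of 0 and unit variances, r = v/(1 + v), where v = q(1 − q)d² and d² = 0.478² = 0.228:

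- q = 5%: v = 0.0475 × 0.228 = 0.011, r = 0.01
- q = 10%: v = 0.09 × 0.228 = 0.021, r = 0.02
- q = 20%: v = 0.16 × 0.228 = 0.037, r = 0.04

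In a plain two-sided Fisher-z test of a correlation at n = 100, which simplifies the planned model, these move the false-positive rate from 5.0% to about 5.1%, 5.5% and 6.4%.

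**Step 4: what it would take to reach the benchmark.** Setting v/(1 + v) = 0.15 gives v = 0.15/0.85 = 0.176, so d = √(0.176/[q(1 − q)]). That is d = 1.93, 1.40 and 1.05 at q = 5%, 10% and 20%. Dividing by 0.478, the full drug effect would have to be about 4.0, 2.9 and 2.2 SD on both outcomes.

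**The case against.** The strongest reply is that this is a minor matter. The affected group is narrow: people who recently started or changed such a drug, for an indication other than migraine, with an effect that is slow to appear. Exclusion 1 removes anyone taking one as a migraine preventive. Exclusions 2, 3, 5, 6 and 18 (other pain, severe cardiac disease, abnormal ECG, uncontrolled blood pressure, psychiatric disorder) remove some of the reasons for starting one. The baseline month absorbs much of a recent start. Nothing in the documents says that these effects are delayed, or that they move sleep and migraine the same way; with opposite directions the spurious correlation would change sign. The comparison with other look-backs is also imperfect. Those in exclusions 12 and 13 are wash-outs for past procedures and injections, while exclusions 1, 10 and 11 concern interfering drugs and look only at current use.

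Most of this stands, and it limits the size of the problem. It does not close the gap: the exclusions are partial safeguards, and none is tied to when a drug was started or changed.

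A reader might infer that recent starters could by themselves generate a correlation as large as the study's target of 0.15. The documents do not support that. At a share of 5% to 10% it would need a full effect of roughly 3 to 4 SD on both outcomes, and even at 20% more than 2 SD.

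**Conclusion.** The gap in the criteria is real: a recent starter or changer is eligible, and the text of the plan offers no means of detecting or adjusting for it. (The study flow chart was not available for this check, so it may list a medication record that the text does not mention.) What follows from the gap is a possibility, not an established bias: a residual drug effect could be attributed to fremanezumab and could contribute to the sleep-migraine association.

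Under the assumptions above, the mean bias is at most about 0.02 to 0.10 SD and the spurious correlation at most about 0.01 to 0.04, for a share of 5% to 20%. All of these figures rest on assumed shares, effect sizes and onset speeds. With few recent starters the bias is smaller still.

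One limit on the absorption argument: it applies to outcomes measured against the 30-day diary baseline, as the aggregated monthly data in Sample Size Justification are. The Insomnia Severity Index is scheduled in the text only at visit 1. If that single score serves as its pre-treatment value, less of a recent start would be absorbed for that outcome.

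The bias is probably small but avoidable, and worth correcting because the correction is cheap.

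**What to change.** 1. Extend inclusion 5 so that the regimen of any such drug must also have been unchanged for a stated period before visit 1. The investigators should set and justify the length.
2. Record at visit 1 the start date and the date of last change for each such drug.
3. Repeat the primary models without participants whose regimen changed within that period, as a prespecified sensitivity analysis. For anyone already enrolled, retrieve the dates and run the same analysis.

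The cost is one clause, two date fields and one extra model run. The downside is that a few candidates are deferred until their regimen has been stable for the required time.
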